9 EFFICACY ANALYSIS

Efficacy analyses will be performed on the Efficacy Evaluable population. All efficacy analyses will be performed by adult vs. pediatric subjects and overall.

9.1 Primary Efficacy Analysis

The primary efficacy variable of SBIs will be analyzed using the Efficacy Evaluable population. The number and percentage of subjects with any SBIs from Week 1 to Week 53 during the IGSC 20% treatment phase, the total number of SBIs, the annualized rate of SBIs for individual subjects, and the rate per person per year of SBIs will be summarized. A listing of SBIs will be provided.

The annualized rate of SBIs for individual subjects will be calculated as:

$$\begin{aligned} & \text{annualized rate of SBIs for the individual subject} \\ &= \frac{\text{number of SBIs for the individual subject}}{\text{duration of exposure in years for the individual subject}} \end{aligned}$$

The SBI rate for all efficacy evaluable subjects will be compared to the recommended standard rate of 1 SBI per person per year. The following hypothesis testing is performed with one-sided test at alpha = 0.01 level:

$$H_0 : \lambda \geq 1 \text{ SBI per person per year}$$

versus

$$H_A : \lambda < 1 \text{ SBI per person per year}$$

Where λ is the SBI rate during IGSC 20% treatment. Occurrence of SBI is assumed to follow the Poisson distribution.

The generalized linear model procedure for Poisson regression with log link will be used to estimate SBI rate per person per year for IGSC 20% and its one-sided 99% upper confidence bound (or equivalently, the upper bound of the two-sided 98% confidence interval). Person-year during IGSC 20% treatment will be calculated for each subject as (duration of exposure in days/365.25), and the natural log-transformed person-year will be used in the generalized linear model as an offset variable. No covariates but the intercept term are included in the model. The estimated intercept term and the upper bound of its two-sided 98% CI will be transformed by using the natural exponential function, to provide the point estimate of the SBI rate per person per year for IGSC 20% and its one-sided 99% upper confidence bound. If the one-sided 99% upper confidence bound is less than 1, then the null hypothesis that the SBI rate per person per year is ≥ 1 will be rejected at one-sided alpha = 0.01 level.

Note the point estimate obtained from the generalized linear model above is the same as the rate of SBIs per person per year directly calculated as follows:

$$\begin{aligned} & \text{rate of SBIs per person per year} \\ &= \frac{\text{total number of SBIs for all subjects}}{\text{total duration of exposure in years for all subjects}} \end{aligned}$$

9.2 Secondary and Other Efficacy Analyses

Secondary and other efficacy variables include the following:

- All infections of any kind (serious/nonserious including acute sinusitis, exacerbation of chronic sinusitis, acute otitis media, pneumonia, acute bronchitis, infectious diarrhea, etc.) which will be recorded as an AE with the Investigator answering the following question affirmatively in the eCRF: “Is this an infection?” (verbatim term delineating infection).
- Number of days on antibiotics (including oral, parenteral, oral plus parenteral, prophylactic and therapeutic). Use of prophylactic antibiotics will be distinguished from antibiotics for treatment of acute infection
- Number of hospitalizations due to infection
- Number of days of work/school/daily activities missed per subject year due to infections and their treatment
- Validated infections documented by positive radiograph, fever (> 38°C oral or > 39°C rectal), culture, *or* diagnostic testing for microorganisms eg, bacterial, viral, fungal or protozoal pathogens (for instance, rapid streptococcal antigen detection test)

For these efficacy variables, the number and percentage of subjects with the events, the total number of events or days, the annualized rate of events or days for individual subjects, and the rate of events or days per person per year will be summarized descriptively. All other efficacy data will be listed as well. Similar to the calculation of the annualized rate of SBIs for individual subjects, the annualized rate of events or days for individual subjects can be calculated as follows:

$$\begin{aligned} & \text{annualized rate of events or days for the individual subject} \\ &= \frac{\text{number of events or days for the individual subject}}{\text{duration of exposure in years for the individual subject}} \end{aligned}$$

The rate per person per year of all infections, validated infections, days on antibiotics, hospitalizations, and days of work/school/daily activities missed will be calculated and the two-sided 95% CI will be provided, using the generalized linear model procedure for Poisson regression with log link similar to that used for the primary efficacy analysis. Similar to the calculation of the rate of SBIs, the rate of events or days per person per year can be directly calculated as follows:

$$\begin{aligned} & \text{rate of events or days per person per year} \\ & = \frac{\text{total number of events or days for all subjects}}{\text{total duration of exposure in years for all subjects}} \end{aligned}$$

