The secondary and other efficacy variables will be summarized descriptively. Annualized rate of all infections, days missed work/school/daily activities, days on antibiotics, and hospitalizations will be calculated and the 95% CI will be provided.

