4 GENERAL STATISTICAL CONSIDERATIONS

Statistical analyses and data presentations will be generated using SAS version 9.4 or higher.

Unless otherwise noted, for continuous variables, descriptive statistics will include the number of non-missing values, mean, standard deviation (SD), median, minimum and maximum. For categorical variables, descriptive statistics will include counts and percentages per category. The hypothesis testing on the primary efficacy variable of the true rate of the SBIs will be tested at 1-sided with $\alpha=0.01$. All other statistical inferences will be tested at 2-sided with $\alpha=0.05$, if applicable.

Unless otherwise noted, all data collected in the eCRFs or electronically transferred (such as central laboratory data) will be presented in data listings. Subjects will be identified in the data listings by subject number (which includes site number) and grouped/sorted by adult vs. pediatric subjects, followed by study phases (Screening/Previous Regimen Phase, IGSC 20% Treatment Stage 1, and IGSC 20% Treatment Stage 2) and visit/time point.

For table summaries, the data will be presented at the scheduled visits according to protocol. Any data collected at the unscheduled visits will be listed.

For table summaries that are presented by adult vs. pediatric subjects and overall, the following age categorization will be used: adults (>16 years) and pediatrics (≤ 16 years).

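### The planned 95% CIs for days on antibiotics and days missed treat each day as an independent event, so they are too narrow if days come in multi-day runs

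*SAP*

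**What the plan says.** SAP 9.2 lists the rates: "The rate per person per year of all infections, validated infections, days on antibiotics, hospitalizations, and days of work/school/daily activities missed will be calculated". Each gets a two-sided 95% CI, "using the generalized linear model procedure for Poisson regression with log link similar to that used for the primary efficacy analysis". SAP 9.1 defines that model as Poisson with log link and a log person-year offset, and adds: "No covariates but the intercept term are included in the model". The rate formula at the end of SAP 9.2 puts total events or total days over total years of exposure.

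For antibiotics, SAP 9.2 counts prophylactic and therapeutic days and then says: "Use of prophylactic antibiotics will be distinguished from antibiotics for treatment of acute infection". It does not say how that distinction carries into the rate or its CI.

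Protocol 5.1.3 promises the interval ("days on antibiotics, and hospitalizations will be calculated and the 95% CI will be provided") and names no method for it. Neither document mentions a scale parameter, robust variance, negative binomial model, bootstrap or clustering by subject. SAP 9 repeats the analyses in subgroups: "All efficacy analyses will be performed by adult vs. pediatric subjects and overall".

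**The concern.** A Poisson model sets the variance equal to the mean. SAP 9.1 makes that assumption for the occurrence of serious bacterial infections, which are separate events. Days on antibiotics and days missed are different, because one infection can produce several consecutive days in the same subject. The model would treat a 7-day course as seven independent observations.

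Both variables are named secondary objectives (Protocol 2.1.2, SAP 2.2.1.2). A reader will take an interval labelled 95% at face value, so the stake is an overstated precision for these two rates, overall and in the adult and pediatric tables.

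**Working it through.** **The plan's own figure.** The only numerical design figure is the power of the primary test (SAP 4.3: 40 person-years, true rate 0.25, null rate 1.0, one-sided 0.01, at least 90%). It reproduces. The rule rejects at 25 or fewer infections, with type I error 0.0076 and power above 0.999. The documents give no figure for the secondary CIs.

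**Inputs.** The model, offset and numerator come from SAP 9.1 and 9.2. The sample of about 60 comes from SAP 4.3. A completer's exposure of 364 days follows from SAP 8.2.1 (51 weekly intervals × 7 + 7). Run lengths, episode rates, dispersion and the share of subjects on prophylaxis are not in the documents, so all are assumed below.

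**Formula.** Let T be total days. The planned SE of the log rate is 1/√T. If episodes are Poisson with run length D, the variance of T is φ times its mean, where φ = E[D²]/E[D]. The correct SE is then √(φ/T), and the nominal 95% interval covers 2Φ(1.96/√φ) − 1.

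**Results.** The simulations used n = 60, two episodes per year, equal subject rates and 20,000 trials. Two thirds of subjects had 364/365.25 years of exposure and one third 0.05 to 0.95 years. The robust CI used a subject-level variance with n/(n−1) and t(n−1).

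| Run length (assumed) | φ | √φ | Coverage, formula | Coverage, simulated | Robust CI, simulated |
|---|---|---|---|---|---|
| 1 day | 1 | 1.00 | 95% | 95.2% | 95.3% |
| 1 or 2 days, evenly | 2.5/1.5 = 1.67 | 1.29 | 87% | 86.8% | 94.9% |
| 2 days | 2 | 1.41 | 83% | 83.6% | 95.1% |
| 3 days | 3 | 1.73 | 74% | 74.6% | 95.2% |
| 5 days | 5 | 2.24 | 62% | 62.0% | 94.9% |
| 7 days | 7 | 2.65 | 54% | 53.7% | 94.9% |
| 7 ± 3 days | (49+9)/7 = 8.29 | 2.88 | 50% | 50.0% | 95.2% |

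**Example.** Take 40 subject-years with two 7-day courses per year, so T = 40 × 2 × 7 = 560 and the rate is 14.0 days per year.
- Planned CI: 14 × exp(±1.96/√560) = 12.9 to 15.2.
- Allowing for runs: 14 × exp(±1.96 × √(7/560)) = 11.2 to 17.4.

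**Sample size.** More subjects do not help, because both SEs shrink together. Simulated Poisson coverage at n = 20 and n = 40 is within about 1 point of n = 60.

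**A separate mechanism.** Subject rates that differ also widen the true SE. With one-day absences and gamma-distributed rates (shape 1), coverage falls to 75.5% with no runs at all. With 3 courses per year of 10 ± 5 days it is 42.0% at equal rates and 24.1% with gamma shape 1.

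**Pooled prophylaxis (conditional).** Suppose 5% to 25% of subjects took antibiotics all year and those days were pooled with treatment days. Poisson coverage would then be about 10% to 13% at n = 60. On a base of two 7 ± 3-day courses per year, the robust CI covers 89.5% (5% users), 93.6% (10%) and 95.4% (25%) at n = 60, but 60.2%, 82.2% and 95.1% at n = 20. At 5% users, 0.95^20 = 36% of groups of 20 contain no user, and no variance estimate from such a group can show what is missing.

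**The case against.** **The intervals are descriptive.** No threshold, comparator or test uses them, and the spread is already visible. SAP 9.2 plans "the total number of events or days, the annualized rate of events or days for individual subjects", and SAP 4 says "descriptive statistics will include the number of non-missing values, mean, standard deviation (SD), median, minimum and maximum". This stands as a limit on the consequence. Those statistics show the clustering, but they do not correct the interval printed beside them.

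**The SAP asks for a similar model, not an identical one.** That wording does not exclude a scale option. None is named, though, and a pre-specified plan should not depend on an unstated one.

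**The size is assumed, and so is part of the direction.** This stands. Episode counts less variable than Poisson could offset the effect, though that is unlikely in practice. If every episode lasts one day and subject rates are equal, the planned CI is correct.

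**Prophylactic days are part of the variable.** This also stands. A reader might infer that the antibiotic CI should be restricted to therapeutic days. The documents do not support that, because Protocol 2.1.2 and 5.1.3 and SAP 2.2.1.2 and 9.2 all include both types. Restriction would also move the estimate. With 5% of subjects on year-round prophylaxis and the rest on two 7-day courses, the total is 0.05 × 365.25 + 0.95 × 14 = 31.6 days per year, against 13.3 for treatment alone.

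Three other stronger readings also fail:
- The 24% and 10% to 13% figures are not expected coverage. They need added between-subject variation or pooled year-round prophylaxis, and the documents state neither.
- The run-length argument does not reach all infections, validated infections or hospitalizations, which are event counts.
- It does not reach the primary analysis of serious bacterial infections.

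**Conclusion.** The SAP is wrong as written on this point, with limited effect. Followed literally, it yields intervals labelled 95% for two named secondary variables that are too narrow by about sqrt(E[D²]/E[D]). This holds if episodes are Poisson or over-dispersed and last more than one day. Differing subject rates would lower coverage further, by a separate route.

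That the model ignores runs is certain from the text. How much it matters depends on run lengths that the documents do not give. No hypothesis test, success rule, sample size or primary result changes. Which antibiotic days the CI covers is a second, smaller gap that needs a statement from the sponsor.

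**What to change.** In SAP 9.2, keep the rate r = total days / total person-years. State that for the two day-count variables the 95% CI uses a subject-level dispersion-robust variance instead of the Poisson model variance. One form is r × exp(± t(0.975, n−1) × SE), with SE = √[n/(n−1) × Σ(y_i − r·t_i)²] / Σy_i, where y_i is days and t_i is years of exposure for subject i. A subject-level bootstrap is another.

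State which antibiotic days each rate and CI covers. Preferably give prophylactic and therapeutic days separately beside the protocol-defined total, without replacing that total and without a minimum number of users as a condition. Note with the total that a few year-round prophylaxis users can make even the robust CI unreliable in the adult and pediatric tables (about 60% coverage at n = 20 with 5% users, under the assumptions above).

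The cost is a few sentences and a short programming step. No new data are needed, because the Protocol 3.6.2 visit procedures already separate prophylactic from treatment use. The protocol-defined rates do not change. The intervals become wider: at n = 60 the median width goes from 1.11 to 1.60 days per year for two 2-day absences a year, and from 2.08 to 6.08 for two 7 ± 3-day courses. With no pooled prophylaxis, robust coverage was 93% to 95% at n = 20.

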10 PK ANALYSIS

The Efficacy Evaluable population will be used for the analyses of trough total IgG concentrations, trough IgG subclasses, and trough antibody titers. The analyses of the mean trough total IgG concentrations will be based on the IgG population. The analyses of serial total IgG concentrations and PK parameters will be based on the PK population.

10.1 Analysis of IgG concentration and dosing data

10.1.1 Analysis of trough total IgG, IgG subclasses, and antibody titers data

Trough concentrations of total IgG during the Screening/Previous Regimen Phase, the IGSC 20% Treatment Stage 1, and the IGSC 20% Treatment Stage 2 will be summarized.

Summaries will be provided for trough concentrations of IgG subclasses (Screening, Baseline/SC#1, SC#13, 24, 36, and Final/Early Termination Visit). Summaries of trough level concentrations of antibody titers against *H. influenzae*, *S. pneumoniae*, and *C. tetani* (tetanus) will also be provided (collected at these same time points).

Trough measles antibody titers (functional assay at Baseline/SC#1, SC#20, and SC#52) will be summarized as an exploratory variable for informational purposes.

All summaries will be provided by study phase and visit for the Efficacy Evaluable population. The summaries will also be provided by adult vs. pediatric subjects and overall.

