- Number of hospitalizations due to infection
- Number of days of work/school/daily activities missed per subject year due to infections and their treatment

Other Variables

- Trough levels of IgG subclasses (IgG1, IgG2, IgG3, IgG4) in specific pre-dose blood samples in all subjects
- Antibody levels for *Streptococcus pneumoniae*, *Hemophilus influenzae*, and *Clostridium tetani* (tetanus)
- PK profile for total IgG (area under the concentration-time curve from 0 to 7 days [$AUC_{0-7 \text{ days}}$], maximum concentration [C_{\max}], and time to reach C_{\max} [t_{\max}]) in adult PI subjects at steady state (after approximately 4 months [16 weeks]) of weekly administration of IGSC 20%
- Trough measles antibody titers (functional assay) are an exploratory variable for informational purposes
- Number of validated infections documented by positive radiograph, fever ($> 38^{\circ}\text{C}$ oral or $> 39^{\circ}\text{C}$ rectal), culture, or diagnostic testing for microorganisms (e.g., bacterial, viral, fungal, or protozoal pathogens [for instance, rapid streptococcal antigen test])

Safety Variables:

- Adverse events (AEs), suspected adverse drug reactions (suspected ADRs), serious AEs (SAEs), and discontinuations due to AEs and SAEs

Note: All local infusion site reactions will be recorded in the eCRF. The subset of local infusion site reactions where the symptoms/signs lead to infusion interruption or discontinuation, require concomitant medication, or have an impact on the general condition of the subject as judged by the Investigator will be considered as AEs.

- Vital signs during clinic visits (temperature [T], respiratory rate [RR], heart rate [HR], systolic blood pressure [SBP] and diastolic blood pressure [DBP]).
- Physical assessments: physical exams will be recorded as normal or abnormal, according to the physician's judgment criteria, and findings will be recorded.
- Laboratory assessments including chemistry, hematology, and urinalysis

Adverse Event Management

Subjects will be carefully monitored for AEs. This monitoring includes clinical and laboratory tests and physical signs. Adverse events should be assessed in terms of their seriousness, severity, and causal relationship to the IP.

Any AE that occurs at any time between the signature of the ICF and last day of the subject's participation in the clinical trial must be reported and recorded in the AE eCRF.

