3.6.2.1 Screening Visit and Previous Regimen Phase

Subjects who initially fail to meet eligibility criteria may be re-screened once upon consultation with the Sponsor. Subjects who fail to meet eligibility criteria upon re-screen are screen failures and will not be eligible to participate in the study.

The Previous Regimen Phase for subjects may be between 4 weeks (for subjects entering study on SCIG) and up to 8 weeks (for subjects entering study on IVIG). At the Screening Visit, if a prospective subject is also being dosed (mandatory in-clinic dosing) with their pIV/pSC infusion, in such instances the Screening Visit also becomes a pIV#1 or pSC#1 Visit which shortens the overall duration of this phase. The duration of this phase is also dependent on the need for the HIV screening results that are required prior to Baseline/Week 1 of Treatment Stage 1, which may take up to 2 weeks to report. Another factor which may impact the duration of this phase is the previous IgG dosing frequency (i.e., weekly, biweekly, once every 3 or 4 weeks) in order to ensure 2 previous regimen C_{trough} blood samples are obtained prior to initiation of IGSC 20% dosing in Treatment Stage 1.

ASSESSMENTS AND PROCEDURES DURING SCREENING VISIT AND PREVIOUS REGIMEN PHASE**Screening Visit Assessments for all subjects**

- Informed consent
- Assess inclusion and exclusion criteria ([Section 3.2](#)) to determine subject eligibility
- Assign subject number
- Medical history (record relevant medical history defined as any history impactful on the subject's condition in terms of current functioning, disability, treatment, or management)
- Demography
- Record specific diagnosis of type of PI, date of diagnosis, and date and dose of current IgG replacement regimen initiated
- AEs (including infusion reactions [see [Section 4.3.1](#) for definitions]), prior and concomitant medications assessments (for antibiotics distinguish between prophylactic use and use for treatment of an episode of infection)
- Full physical exam (excludes breast and genitourinary exam)
- Record any SBIs (defined in [Appendix 3](#)) and hospitalizations due to infections (*if this occurs during the Screening/Previous Regimen Phase, the subject will be a Screen Failure*)
- Record non-serious infections (by category) and antibiotic treatment.

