These include infections of any kind including for example acute sinusitis, exacerbation of chronic sinusitis, acute otitis media, pneumonia, acute bronchitis, infectious diarrhea, etc., which will be recorded as an AE with the Investigator answering the following question affirmatively in the eCRF: "Is this an infection? (verbatim term delineating nature of infection). Also record validated infections documented by positive radiograph, fever (> 38°C oral or > 39°C rectal), culture, *or* diagnostic testing for microorganisms e.g., bacterial, viral, fungal, or protozoal pathogens (for instance, rapid streptococcal antigen test). The specific evaluations performed to validate infections must be recorded in the eCRF.
- Height and weight
- Vital signs (T, RR, HR, SBP, DBP)
- Record results of most recent chest X-ray within 12 months (A chest X-ray will be necessary if not performed within 12 months of the Screening visit for adult subjects only as permitted per local requirements.) Note: at least one radiographic view (anterior-posterior [AP] or posterior-anterior [PA] is required)
- Sample for IgG subclass levels, and antibody titers for bacterial pathogens (*H. influenzae*, *S. pneumoniae*, *C. tetani* [tetanus])
- Blood and urine samples for clinical laboratory assessments (e.g., clinical chemistry, hematology, urinalysis, pregnancy testing) (see [Section 3.6.3](#)).
 - Hemoglobin, hematocrit, platelets, red blood cell count including red blood cell morphology, white blood cell count with differential; absolute reticulocyte count (ARC)

- Additional Special Tests: haptoglobin
- HIV NAT test sample
- Sodium, potassium, creatinine, chloride, calcium, BUN, bicarbonate, albumin, lactate dehydrogenase (LDH), AST, ALT, alkaline phosphatase (ALP), glucose, total bilirubin, indirect bilirubin
- Serum pregnancy test (potential child-bearing females only)
- Urinalysis: pH, protein, glucose, ketones, bilirubin, nitrites, urobilinogen, blood, leukocyte esterase (with microscopic examination of urine sediment if abnormal)

For subjects who will also receive a previous regimen SCIG or IVIG dose at the Screening Visit, perform the following:

- Blood sample for previous regimen IgG level (C_{trough} for subjects receiving pIV#1/pSC#1)
- pIV/pSC dose in the clinic (mandatory)

For subjects who will NOT receive a previous regimen SCIG or IVIG dose at the Screening Visit, schedule a pIV#1/pSC#1 Visit during this stage.

Previous Regimen Phase pIV or pSC Visit #1 or #2

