5.1.4 Pharmacokinetic Analysis

Trough concentrations of total IgG during the Screening/Previous Regimen Phase and the IGSC 20% Treatment Stages will be summarized by week for the efficacy evaluable population. Mean trough for IGSC 20% treatment phase will be calculated as the average of

all steady state trough concentrations measured during the IGSC 20% Treatment Stage 2, i.e., IgG trough levels measured at the following visits: SC#17, #18, #20, #24, #28, #32, #36, #40, #44, #48, #52, and #53. Comparison will be made to the mean of 2 troughs for previous IgG treatment (either IVIG or other SCIG products) obtained from the Screening/Previous Regimen Phase. Mean trough data will be summarized. Mean trough summary and analysis will be based on the IgG population.

For samples collected after SC#14 infusion (start of Treatment Stage 2), total IgG concentrations will be summarized by time point. For subjects in the PK subset with an IgG PK profile, individual and mean/median IgG concentrations vs. time curves will be plotted. PK parameters for total IgG including $AUC_{0-7days}$, C_{max} , and t_{max} will be determined by noncompartmental model using WinNonlin software. All PK parameters will be tabulated and summarized descriptively. The analyses will be based on the PK population.

Summaries will be provided for average trough concentration of IgG subclasses (Screening, Baseline, before the 13th, 24th, 36th IGSC 20% infusion, and Final Visit). Summaries of average trough level concentration of antibody titers against *S. pneumoniae*, *H. influenzae*, and *C. tetani* (tetanus) will also be provided (collected at these same time points).

Trough measles antibody titers (functional assay at Baseline, SC#20 Visit, and SC#52 Visit) are an exploratory variable for informational purposes.

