10 APPENDICES

Appendix 1 Schedule of Study Procedures

Procedures and Evaluation Visit Designations:	Previous Regimen Phase			IGSC 20% Treatment Stage 1			IGSC 20% Treatment Stage 2			Final Visit (Week 53)/ Early Termination 1 Week post last IGSC 20% Dose
	Screening ^a	pIV#1 ^a /pSC#1 ^a	pIV#2	Baseline/ SC#1	SC#2 & 3	SC#5, 9, 13	SC#17	SC#18 in clinic only for PK subset	SC#20, 24, 28, 32, 36, 40, 44, 48, 52	
Study Weeks				Week 1	Weeks 2&3	Weeks 5, 9, 13	Week 17	Week 18	Weeks 20, 24, 28, 32, 36, 40, 44, 48, 52	Week 53
Informed consent/assent (if applicable)	X									
Inclusion/exclusion criteria (confirm eligibility) ^b	X			X ^c						
Medical history, demography	X									
Record specific diagnosis of type of PI	X									
Full physical exam ^d	X			X ^c		SC#13 ^c			SC#24 ^c , SC#36 ^c	X
Weight ^e	X			X ^c		X ^c	X ^c	X ^c	X ^c	
Height	X			X		SC#13			SC#24, SC#36	X
Record results of most recent chest X-ray within 12 months ^f	X ^f									
Vital signs	X	X	X	X ^c		X ^c	X ^c	X ^c	X ^c	X
Record any serious bacterial infections (defined in Appendix 3), hospitalizations due to infections	X	X	X	X	X	X	X	X	X	X
Record non-serious infections as AEs & antibiotic treatment	X	X	X	X	X	X	X	X	X	X
Record days lost from work/school/daily activities due to infections and treatment		X	X	X	X	X	X	X	X	X
Laboratory assessments (chemistry, hematology, special tests, urinalysis) ^g	X			X ^c		SC#13 ^c			SC#24 ^c , SC#36 ^c	X ^c
Serum pregnancy test ^h	X	X ^{c, g}								X
Urine pregnancy test ^h (at site)				X ^c						
Trough (pre-dose) PK IgG sampling	X	X ^c	X ^c	X ^c	SC#2 only ^c	X ^c	X ^c	X ^c	X ^c	X ^c
Sample for IgG subclass levels & antibody titers for bacterial pathogens (H. influenzae , S. pneumoniae , C. tetani [tetanus])	X			X ^c		SC#13 ^c			SC#24 ^c , SC#36 ^c	X ^c

Procedures and Evaluation Visit Designations:	Previous Regimen Phase			IGSC 20% Treatment Stage 1			IGSC 20% Treatment Stage 2			Final Visit (Week 53)/ Early Termination 1 Week post last IGSC 20% Dose
	Screening ^a	pIV#1 ^a /pSC#1 ^a	pIV#2	Baseline/ SC#1	SC#2 & 3	SC#5, 9, 13	SC#17	SC#18 in clinic only for PK subset	SC#20, 24, 28, 32, 36, 40, 44, 48, 52	
Study Weeks				Week 1	Weeks 2&3	Weeks 5, 9, 13	Week 17	Week 18	Weeks 20, 24, 28, 32, 36, 40, 44, 48, 52	Week 53
Blood draw for trough measles antibody titer				X ^c					SC#20, SC#52 ^c	
HIV NAT testing	X									
Collection of virus safety retain samples ^l				X ^c						
Previous (p)IV/SC infusions		X	X							

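### For IVIG entrants screened away from a dosing day, the Screening IgG-subclass and bacterial-antibody sample is not a trough, yet the SAP summarises it as one

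*SAP*

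**What the plan says.** **The label.** The SAP and the protocol both call the Screening value a trough.

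- SAP 10.1.1: "Summaries will be provided for trough concentrations of IgG subclasses (Screening, Baseline/SC#1, SC#13, 24, 36, and Final/Early Termination Visit". The titers follow at the same time points: "Summaries of trough level concentrations of antibody titers against" the three bacterial pathogens.
- Protocol 5.1.4: "Summaries will be provided for average trough concentration of IgG subclasses (Screening, Baseline" and the later visits.
- Protocol Synopsis, Other Variables, ties the subclass variable to dosing: "Trough levels of IgG subclasses (IgG1, IgG2, IgG3, IgG4) in specific pre-dose blood samples in all subjects".

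**The sampling.** Protocol 3.6.2.1 sets no timing against the previous IgG dose.

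- Under "Screening Visit Assessments for all subjects" it lists "Sample for IgG subclass levels, and antibody titers for bacterial pathogens", with no pre-dose condition.
- The same section expects some subjects to attend Screening undosed: "For subjects who will NOT receive a previous regimen SCIG or IVIG dose at the Screening Visit, schedule a pIV#1/pSC#1 Visit during this stage". The list for that later visit has no subclass or titer sample.
- In Appendix 1 the row "Sample for IgG subclass levels & antibody titers for bacterial pathogens" is marked at Screening, Baseline, SC#13, SC#24, SC#36 and the Final Visit. It is blank at pIV#1/pSC#1 and at pIV#2.
- Section 3.6.3.2 says that the Baseline sample precedes the first IGSC 20% dose, but gives no timing for Screening.

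**The concern.** Protocol 1.4.1 describes IVIG as producing a marked peak that declines over a 3 to 4 week interval. A sample taken before the end of that interval lies above the trough. If such values are pooled with true troughs in one column labelled trough, the column mean is too high. IGSC 20% troughs set beside it would then look lower than they should, or a real rise would be masked.

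Total IgG does not have this weakness. The visit text in 3.6.2.1 draws total IgG at Screening only from subjects dosed there, and SAP 10.1.2 takes the previous-regimen mean from pIV#1 and pIV#2, or from pSC#1 and Baseline. Subclasses and bacterial titers have no such safeguard. Measles titers are not drawn at Screening, so the point does not apply to them.

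**Working it through.** The plan gives no figure to reproduce. The check has two parts: whether anything else supplies the missing trough, and how large the error could be.

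**1. Does another sample or rule fill the gap?**

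- *Baseline, IVIG entrants.* Protocol 3.3.2 and 3.6.2.2 start IGSC 20% 7 days after the last IVIG dose. That sample falls early in an IVIG cycle and is not an IVIG trough.
- *Baseline, SCIG entrants.* Baseline falls at the end of the SCIG dosing interval, so it is a previous-regimen trough.
- *SAP 4.1.1.2.* Its examples of invalid values are hemolysed samples and planned troughs drawn after infusion. A sample taken mid-interval at an undosed visit is neither.

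An IVIG entrant screened off-dose therefore has no scheduled previous-regimen trough for any subclass or bacterial antibody.

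**2. When in the cycle can an off-dose Screening fall?**

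Screening to Baseline is at most 8 weeks (protocol 3.3.2, 3.6.1 and Appendix 1, footnote h).

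- *4-weekly IVIG:* pIV#1 to pIV#2 takes 4 weeks and pIV#2 to Baseline takes 1 week. Screening can precede pIV#1 by at most 8 − 4 − 1 = 3 weeks, so it falls at least about 28 − 21 = 7 days after the preceding infusion. (Using the permitted 6-day gap before SC#1 moves this by one day.)
- *3-weekly IVIG:* 8 − 3 − 1 = 4 weeks, so the whole 21-day cycle is open.

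In both cases the time remaining to the trough runs from 0 to about 21 days.

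**3. Size under assumed decay**

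Assumptions, none from the documents: one exponential decline with half-life h of 21 to 35 days, and Screening uniformly distributed over those 21 days. With k = ln 2 / h:

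- average value / trough = (e^(21k) − 1) / (21k)
- highest value / trough = e^(21k)

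| h (days) | 21k | average / trough | highest / trough |
|---|---|---|---|
| 21 | 0.693 | 1.44 | 2.00 |
| 28 | 0.520 | 1.31 | 1.68 |
| 35 | 0.416 | 1.24 | 1.52 |

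An affected value averages 24% to 44% above trough, and is at most about 1.5 to 2.0 times the trough.

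**4. A proxy from the protocol's own data**

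Table 1-1 gives mean SC and IV total IgG troughs at equal dose. The smallest ratio is 890/860 = 1.035 and the largest is 792/647 = 1.224. If a nearly flat SC level approximates the IV cycle average (this assumes similar bioavailability), a randomly timed IV sample lies about 4% to 22% above trough.

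**5. SCIG entrants**

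A one-compartment steady-state model was used, with an assumed absorption half-life of 1 to 3 days and elimination half-life of 21 to 35 days. A random-time sample averages about 2% to 7% above trough for weekly SCIG and 7% to 21% for two-weekly SCIG. Protocol 1.4.1 likewise describes SCIG levels as much less variable.

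**6. Effect on the column mean**

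The share of subjects screened off-dose is not given. If true troughs are alike across subjects, each 10% of the column made up of affected IVIG entrants raises its mean by about 0.10 × 24% = 2.4% to 0.10 × 44% = 4.4%.

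**The case against.** The strongest reply is that no planned comparison is biased. Subclasses and titers are listed among the other variables and are summarised by phase and visit, with Screening as its own column. SAP 4.1 defines baseline as the last value before SC#1, not the Screening value. The only planned comparison of troughs before and after the switch is for total IgG, and its samples are properly timed. This stands and limits the consequence: the error lies in a mislabelled descriptive column and in the informal contrast that readers will draw from it.

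Three further limits also stand.

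- The number affected may be small, because Screening may coincide with pIV#1.
- A reader might infer from Appendix 1 that the missing pre-dose footnote (c) at Screening singles this sample out as untimed. It does not: the Screening cell of the total IgG trough row lacks that footnote too. The point rests on the visit text and on the blank cells at pIV#1/pSC#1 and pIV#2.
- SAP section 1 cites protocol Version 3.0 of 21 Mar 2017, whereas the amendment summary in the protocol under review is for Version 2.0. A later change to sample timing cannot be excluded, although the SAP still lists Screening.

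None of these makes an off-dose IVIG sample a trough.

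**Conclusion.** The point holds for IVIG entrants whose Screening Visit is not pIV#1. Followed as written, the plan reports their untimed subclass and bacterial-antibody values as troughs, contrary to the protocol's own description of the variable as pre-dose. The direction of the expected bias is upward. Its size rests on assumptions: about 24% to 44% per affected value with a half-life of 21 to 35 days and uniform timing, or 4% to 22% by the Table 1-1 proxy, which concerns total IgG rather than subclasses or specific antibodies. The error is near zero when Screening falls just before the next dose.

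Two stronger readings are tempting and are not supported.

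- Averaging over a full 28-day cycle would give an excess of 34% to 64%, with values up to 2.5 times the trough soon after infusion. The 8-week limit rules out about the first week of a 4-weekly cycle.
- A reader might extend the claim to every subject not dosed at Screening. For weekly SCIG the error is only about 2% to 7%, and all SCIG entrants have a previous-regimen trough at Baseline.

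The serious bacterial infection analysis and the total IgG trough comparison are unaffected. The point should be corrected, but it does not bear on the trial's main conclusions.

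**What to change.** **Protocol, for subjects not yet screened.** First confirm the schedule in Version 3.0. If it is unchanged, amend 3.6.2.1, 3.6.3.2 and Appendix 1 so that the subclass and titer sample is taken at the pre-dose pIV#1/pSC#1 draw, together with the total IgG trough, and mark it explicitly as pre-dose. Nothing moves when Screening coincides with that visit. The cost is a short amendment and one tube moved to a visit where blood is already drawn; no visit or sample is added.

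**SAP 10.1.1, in any case.** Restrict the pre-treatment trough summary to samples confirmed as drawn before a previous-regimen dose due that day, plus Baseline for SCIG entrants. Report off-dose Screening values separately as untimed, with days since the last IgG dose and entry route (IVIG or SCIG). Protocol 3.4 asks for all IgG treatments in the 12 months before screening, so the interval can be derived where infusion dates were captured.

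The price is a smaller n in the pre-treatment trough column. No collected data are discarded. If enrolment is complete, the SAP change alone is sufficient.
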